### **2.2.3 Pharmacokinetic variables**

The PK variables are plasma concentrations of BKZ and CZP.

### **2.2.4 Pharmacodynamic variables**

The pharmacodynamic (PD) variables are the blood or blood derivative (eg, plasma) concentrations of cytokines and chemokines of relevance to interleukin-17A (IL-17A) or interleukin-17F (IL-17F) signaling pathway, tumor necrosis factor (TNF) signaling pathway, AS biology, and bone metabolism. Additional variables may include, but will not be limited to, serum complement concentrations and mononuclear cell subtypes.

### **2.2.5 Immunological variables**

Anti-BKZ antibody and anti-CZP antibody (collectively anti-drug antibody [ADA]) detection prior to and following study treatment will be evaluated.

### **2.2.6 Nonhereditary pharmacogenomic variables**

Where local regulations permit, blood and urine will be collected and stored for up to 20 years to allow for potential exploratory analyses of ribonucleic acid, proteins, and metabolite biomarkers relevant to AS, bone metabolism, and the inflammatory and immune response processes. The nature and format of these tentative analyses will be determined at a later stage and will not form part of the CSR and are not further described in this SAP.

### **2.2.7 Pharmacogenetic variables**

Additional blood samples will be collected from subjects who consent to participate in the pharmacogenetic substudy and stored at -80°C for up to 20 years. Pharmacogenetic biomarkers may be measured to evaluate the relationship to response to treatment with BKZ, AS disease biology, bone metabolism, and inflammatory and immune response processes. The nature and format of these tentative substudy analyses will be determined when the results of the main study are made available. The results of these analyses will not form part of the CSR and are not further described in this SAP.

## 2.3 Study design and conduct

AS0013 is a multicenter, randomized, subject-blind and investigator-blind, parallel-group study to evaluate the efficacy and safety of BKZ compared to CZP in adult subjects with active adult-onset AS.

It is planned that at least 60 subjects will be randomized to 1 of 2 treatment arms in a 2:1 ratio and will receive either BKZ or CZP up to Week 44 (final dose of investigational medicinal product [IMP]).

The study will include a Screening Period of 2 to 4 weeks, a 12-week Treatment Period, a 36-week Treatment Extension Period, and a 20-week Safety Follow-up (SFU) Period (starting after the final dose of IMP). Therefore, the maximum duration of the study will be 68 weeks.

At the start of the Treatment Period, eligible subjects will be randomized in a 2:1 ratio to receive the following blinded study treatments:

- BKZ 160mg sc Q2W from Week 0 through Week 10. In addition, subjects will receive 1 placebo injection at Baseline (Visit 2), Week 2 (Visit 3), and Week 4 (Visit 3) in order to maintain the blind versus the CZP loading dose at these visits.
- CZP 400mg sc Q2W at Weeks 0, 2, and 4 (loading dose) followed by CZP 200mg sc Q2W at Weeks 6 to 10.

After completing the 12-week Treatment Period, subjects will enter a 36-week Treatment Extension Period and will receive the following treatments:

- Subjects randomized to BKZ during the Treatment Period will receive BKZ 320mg sc every 4 weeks (Q4W) from Week 12 to Week 44.
- Subjects randomized to CZP during the Treatment Period will receive CZP 400mg Q4W from Week 12 to Week 44.

Subjects not responding to treatment during the Treatment Period will be withdrawn from the study as per Investigator's discretion and will not enter the Treatment Extension Period.

In a substudy of AS0013, a PET-MRI or PET-CT scan of the entire spine will be performed at selected sites in approximately 25 subjects at Screening and during the study at Week 12 and Week 48 or Early Withdrawal Visit if PET positive lesions were observed in the previous scan.

All subjects who complete the study or who discontinue from the study early, including those withdrawn from the IMP treatment, will have a SFU Visit at 20 weeks after their final dose of IMP.

Three unblinded interim analyses will be conducted:

- Interim Analysis 1 (IA1): when approximately 45 subjects have completed the Week 4 visit during the Treatment Period.
- Interim Analysis 2 (IA2): when all subjects not participating in the PET-MRI/PET-CT sub-study have completed the Week 12 visit at the end of the Treatment Period.
- Interim Analysis 3 (IA3): when the last randomized subject has completed the Week 12 visit at the end of the Treatment Period, or the subject has discontinued prematurely from the study.

Further details on the interim analyses planned for this study are included in the interim SAP.

A data monitoring committee (DMC) will review the data on an ongoing basis. The composition and roles of the DMC are described in a separate DMC Charter. The analyses required and data to be presented are described in a separate DMC SAP.

## 2.4 Determination of sample size

A sufficient number of subjects will be enrolled to ensure that at least 60 subjects are available in the main study at Week 12 to compare the change from Baseline in ASDAS between BKZ and CZP. This will also provide at least 25 subjects enrolled in the PET-CT or PET-MRI substudy from multiple sites. Subjects will be randomized in a 2:1 ratio to receive BKZ or CZP respectively.

The sample size was calculated to provide at least 80% power to detect a difference between treatment groups in the mean change from Baseline in ASDAS at Week 12 of 0.89 (group mean change from Baseline for CZP and BKZ being -1.78 and -2.67 respectively) with a common standard deviation (SD) of 1.17 using frequentist methods for the comparison of the treatment group mean change from Baseline in ASDAS at Week 12 with Baseline ASDAS as a covariate (Overall and Starbuck, 1979).

The correlation between Baseline and Week 12 raw ASDAS was assumed to be 0.35. Note that the informative prior for the model intercept to be used in the Bayesian modelling of the primary efficacy variable, given by  $\beta_{CZP} \sim \text{Normal}(-1.78, \text{var}=0.0605)$ , contributes an effective sample size of approximately 20 CZP subjects. Prior data conflict will be investigated, and a vague prior will be used for the model intercept coefficient if prior data conflict is evident.

Note that a clarification regarding the sample size for this study was provided in protocol amendment 3. As indicated above, the planned sample size of at least 60 subjects provides sufficient power to detect meaningful treatment differences in the primary efficacy variable whilst also providing at least 25 subjects for the PET-MRI or PET-CT substudy. However, due to complexities in the initiation of sites capable of performing PET-MRI or PET-CT scans, more than the planned 35 non-PET-MRI/CT substudy subjects were screened and randomized before it was possible to close enrolment at the sites not participating in the substudy. Owing to the novelty of the PET-MRI/CT outcomes within this disease area, it is considered important to ensure at least 25 evaluable subjects are included in the assessment of this exploratory objective to maximize the possibility of identifying the salient factors or variables that might differ between the treatment groups and, therefore, the total sample size is increased to at least 72 subjects. This sample size increase will not negatively impact the power to detect a difference in the primary efficacy variable at Week 12 (ie, it will remain >80%), but will ensure that the target number of subjects are included in the exploratory analysis of changes in bone formation at Week 12 and Week 48. Since the analyses of PET-MRI/CT data are exploratory and treatment effect sizes are unknown, formal power calculations were not performed. Clinical expertise does, however, indicate that a sample size of at least 25 subjects in the substudy will characterize broad differences between treatment groups.

## 3 DATA ANALYSIS CONSIDERATIONS

### 3.1 General presentation of summaries and analyses

Statistical evaluation will be performed by PAREXEL and supervised by the Exploratory Statistics and Global Statistical Sciences Departments of UCB.

The datasets will follow the UCB analysis data model data specifications.

All analyses will be performed using SAS version 9.2 or higher (SAS Institute, Cary, North Carolina, USA). R Version 2.10.1 (R Development Core Team) or later, and/or OpenBUGS Version 3.0.6 or later may be used for complementary analysis.

Descriptive statistics will be used to provide an overview of the Baseline, efficacy, PD, PK and safety results. Formal statistical testing will be conducted for the primary and secondary efficacy variables only in this study. Other efficacy variables will be summarized descriptively by treatment group.

Continuous variables will be summarized by treatment, visit and time point (where applicable) including number of subjects (n), mean, SD, median, minimum and maximum. First and third quartiles (Q1 and Q3 respectively) and 95% confidence intervals (CI) for the mean will also be included where stated in the SAP.

Categorical variables will be summarized by treatment, visit and time point (where applicable) with frequency counts and percentages. Geometric coefficient of variation (geoCV), geometric mean and 95% CI for the geometric mean will also be presented in the descriptive statistics for the PK concentration and hs-CRP data. In all outputs the 95% confidence limits will be restricted to the possible values that the variable can take.

When reporting relative frequencies or other percentage values, the following rules apply:

- For values where all subjects fulfill certain criteria, the percentage value will be displayed as 100
- For values where the absolute frequency is zero, there will be no percentage displayed at all
- All other percentage displays will use 1 decimal place
- Unless otherwise stated, the denominator for the percentages will be based on the number of subjects in the respective analysis set and treatment group.

Percentages displayed based on continuous data (eg, percentage changes from Baseline) will be displayed to 1 decimal place.

When reporting descriptive statistics, the following rules will apply in general (with the exception of PK and hs-CRP data, for which additional rules are stated below):

- n will be an integer
- Mean, SD, median and CIs will use 1 decimal place more (or 1 more significant figure, depending on the original data reporting format) than the original data
- Coefficient of variation will be reported as a percentage to 1 decimal place

- Minimum and maximum will be reported using the same number of decimal places as the original data
- If no subjects have data at a given time point, then only n=0 will be presented. If n<3, then only n, minimum and maximum will be presented. If n=3, then only n, median, minimum and maximum will be presented. The other descriptive statistics will be left blank.

When reporting individual values and descriptive statistics for PK concentration and hs-CRP data, the following rules will apply with regard to rounding and precision:

- Individual values will be reported to the same level of precision as received from the bioanalytical laboratory
- Descriptive statistics will be reported to the same level of precision as the individual data for the minimum and maximum, to 1 additional significant figure for the mean (arithmetic and geometric), median, Q1, Q3, SD, and to 2 additional significant figures for the 95% CI for the geometric mean
- The geoCV will be reported as a percentage to 1 decimal place

All statistical tests will be carried out 2-tailed at the 5% level of significance unless otherwise stated. The following rules will apply for the presentation of any results relating to inferential statistical analysis:

- P-values will be presented to 4 decimal places; p-values less than 0.0001 will be presented as “<0.0001” and p-values greater than 0.9999 will be presented as “>0.9999”
- Posterior probabilities associated with the Bayesian analyses will be presented as percentages to 1 decimal place
- Means, SDs, medians, 95% credible intervals and highest posterior density intervals obtained from the Bayesian analyses will be presented to 1 decimal place

All statistical output will be presented in statistical appendices where appropriate.

Time to response data (Section 8.3.2.2) will be analyzed for the Treatment Period and across the study (Treatment Period + Treatment Extension Period). All other data tabulations will be performed by treatment group, visit and time point (where applicable) and no separate analyses based on study period will be presented.

The treatment groups will be displayed as follows in the TFLs, where BKZ refers to bimekizumab and CZP refers to certolizumab pegol:

- BKZ
- CZP

Data listings containing all documented data and all derived data will be generated. Subjects enrolled in the PET-MRI/PET-CT substudy will be flagged in the data listings.

If Study Data Tabulation Model (SDTM) controlled terminology (CT) is defined for selected variables, it will be displayed similarly in the TFLs.

Yes/No responses will be presented as Y/N consistent with the YN CT and Male and Female will be replaced with M/F respectively in the TFLs.

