15.2 General statistical considerations

Statistical evaluation will be performed by PAREXEL and supervised by the Exploratory Statistics and Global Statistical Sciences Departments of UCB.

All analyses will be performed using SAS® Version 9.2 or later (SAS Institute, Cary, NC, USA) or R Version 2.10.1 (R Development Core Team) or later, or OpenBUGS Version 3.0.6 or later.

Descriptive statistics will be used to provide an overview of the Baseline, efficacy and safety results. For categorical parameters, the number and percentage of subjects in each category will be presented by treatment group. The denominator for the percentages will be based on the number of subjects appropriate for the purpose of analysis. Unless otherwise noted, all percentages will be expressed to 1 decimal place. For continuous parameters, descriptive statistics will include n, mean, standard deviation (SD), median, minimum, and maximum. Two-

sided 95% confidence intervals, geometric means, and coefficient of variation (CV) will be presented for selected variables as appropriate.

Baseline for each assessment is defined as either the value obtained at Baseline (Visit 2) or the last available value obtained prior to treatment administration at the Screening Visit (Visit 1) (details to be specified in the SAP).

Formal statistical testing will be conducted for this study for the primary efficacy variable. Other efficacy variables will be summarized descriptively by treatment group. Additional exploratory analyses will be conducted as deemed appropriate.

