### **3.5.3 Safety Set**

The Safety Set (SS) will consist of all randomized subjects who receive at least 1 dose (full or partial) of the IMP. The safety analysis will be conducted on the SS.

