#### **8.2.1 ASDAS Disease Activity States and Improvement**

##### **8.2.1.1 Derivation of ASDAS Disease Activity States and Improvement**

Cut-offs for 4 disease activity states based on ASDAS will be defined for each subject at Baseline and at each post-Baseline visit as follows:

- ASDAS-Inactive Disease (ASDAS-ID): ASDAS < 1.3
- ASDAS-Moderate Disease activity (ASDAS-MD): ASDAS  $\geq$  1.3 to < 2.1
- ASDAS-High Disease activity (ASDAS-HD): ASDAS  $\geq$  2.1 to  $\leq$  3.5
- ASDAS-Very High Disease activity (ASDAS-vHD): ASDAS > 3.5

In addition, the following cut-offs for 2 levels of improvement in ASDAS will be defined for each subject at each post-Baseline visit based on the change from Baseline in ASDAS:

- ASDAS Clinically Important Improvement (ASDAS-CII): a reduction (improvement) from Baseline in ASDAS  $\geq$  1.1 units
- ASDAS Major Improvement (ASDAS-MI): a reduction (improvement) from Baseline in ASDAS  $\geq$  2.0 units

ASDAS-Inactive Disease (ASDAS-ID) and ASDAS-Major Improvement (ASDAS-MI) at Week 12 are the secondary efficacy variables defined for this study. Subjects with missing ASDAS at Week 12 will not be classified in terms of their ASDAS disease activity state or improvement according to the above definitions.

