above) will be summarized by treatment group (number and percentage of subjects) at each post-Baseline visit, based on the PK-PPS. This tabulation will count the number of subjects at each post-Baseline visit who fulfill at least 1 of the above defined criteria for treatment-induced positivity; subjects will be counted in the numerator based on the earliest visit at which 1 of these criteria is fulfilled. At other visits, subjects will be counted in the denominator (assuming a measurement is available). For all tabulations, percentages will be based on the number of observations at each visit.

Separate listings will be presented (based on the PK-PPS) showing the BKZ and CZP concentrations and ADA measurements in the same output in adjacent columns. The listing will include the BKZ and CZP concentration, ADA status (ACP or BCP) and confirmatory assay results if applicable (NCP or CP), together with the titre for results that are CP. In addition, the time since the previous administration of IMP will be reported (in days).

Finally, individual subject plots (based on the PK-PPS) will be presented displaying ADA titre, BKZ and CZP concentrations overlaid on the same figure using a semi-logarithmic scale.

The rules for handling values that are BLQ in the BKZ and CZP concentration data are described in [Section 4.2.4](#). For the ADA data, any negative results for which there are no titres available at a specific visit will be substituted with 0.001 for the purpose of the figure.

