## 11 SAFETY ANALYSES

All analysis of safety variables will be performed using the SS.

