### **11.3 Clinical laboratory evaluations**

Laboratory data (chemistry, hematology, and urinalysis) and changes from Baseline (if applicable) for numeric variables will be listed by treatment group and visit. Any laboratory variables that are BLQ or ALQ will be handled as described in [Section 4.2.3](#). Values outside the reference range for the numeric variables will be flagged in the listings and, in addition, will be listed separately. The reference ranges will also be reported in the listings.

Chemistry and hematology variables presented in [Table 11-1](#) will be summarized by treatment group at each visit, for both observed values and changes from Baseline. Figures of mean and mean change from Baseline will be presented by treatment for the absolute neutrophil count (ANC). All treatment groups will be overlaid on the same plot and the plot will include the error bars based on the SD (ie, mean +/-SD).

Laboratory variables will be grouped according to the laboratory function panel and categorized as normal, high or low, if applicable, based on the reference range supplied by the analytical laboratory. For selected variables that are identified in [Table 11-1](#), the change in category from Baseline will be presented in shift tables at all post-Baseline visits.

The number and percentage of subjects with treatment-emergent markedly abnormal (TEMA) values will be tabulated by treatment group and visit. Markedly abnormal laboratory values will generally be defined as those categorized as Grade 3 or Grade 4 as per the Rheumatology Common Toxicity Criteria (RCTC). Communication with the lead author of the RCTC publication has revealed that the reference ranges for absolute lymphocyte counts (ALC) are in error, therefore ALC criteria will follow the ranges defined as per the Common Terminology Criteria for Adverse Events (CTCAE) Version 4.03 (United States Department of Health and Human Services, 2010). Additional laboratory variables (not present in the RCTC publication) will also be categorized as per the CTCAE Version 4.03. The criteria for identifying TEMA values are presented in [Table 14-5](#) and [Table 14-6](#) for hematology and chemistry values respectively.

Laboratory measurements meeting the criteria for TEMA will be listed separately for hematology and chemistry. The listings will include all measurements for any variable with at least one TEMA result for each subject.

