## 11.4 Vital signs, physical findings, and other observations related to safety

### 11.4.1 Vital signs

The following vital signs measurements will be obtained:

- Pulse rate
- Systolic and diastolic blood pressure
- Temperature

A by-subject listing of all vital sign measurements and changes from Baseline will be presented by treatment group and visit. The listing will include a flag for measurements identified as TEMA/potentially clinically significant (PCS) as calculated by the criteria outlined in [Table 14–8](#). Body weight will be included in the listing.

Descriptive statistics will be reported for all vital sign measurements. Observed values and changes from Baseline will be summarized by treatment group for each vital signs variable and visit.

Figures of mean change from Baseline over time will be presented for each variable by treatment group.

The number and percentage of subjects with TEMA/PCS vital sign values will be summarized by treatment group at each visit. The denominator for the percentages will be the number of subjects with a non-missing measurement for the variable at the specific visit.

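### The by-visit table of markedly abnormal laboratory values (SAP 11.3) has no denominator of its own, so the SAP 3.1 default applies and late-visit percentages are diluted by attrition, unlike the vital-sign and QTcF tables

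*SAP*

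**What the plan says.** The general rule in SAP 3.1 is: "Unless otherwise stated, the denominator for the percentages will be based on the number of subjects in the respective analysis set and treatment group". SAP 11 assigns the analysis set: "All analysis of safety variables will be performed using the SS". SAP 3.5.3 defines that set: "The Safety Set (SS) will consist of all randomized subjects who receive at least 1 dose (full or partial) of the IMP". Membership is thus fixed at the first dose and requires no laboratory sample at any visit.

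For laboratory data, SAP 11.3 says: "The number and percentage of subjects with treatment-emergent markedly abnormal (TEMA) values will be tabulated by treatment group and visit". No denominator is given there, in the rest of 11.3, in SAP 14.6, or in Tables 14-5 and 14-6.

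Three other places replace the default. SAP 11.4.1 says of the vital-sign abnormality table: "The denominator for the percentages will be the number of subjects with a non-missing measurement for the variable at the specific visit". SAP 11.4.2 uses the same rule for the QTcF categories. SAP 10 says of the anti-drug antibody tables: "For all tabulations, percentages will be based on the number of observations at each visit".

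Protocol 15.2 is general: "The denominator for the percentages will be based on the number of subjects appropriate for the purpose of analysis". SAP 1 defers to the protocol only where the SAP itself is silent, and SAP 3.1 is not silent.

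**The concern.** A by-visit abnormality percentage is normally read as a rate among people who were measured. Under the default, a subject who left before Week 24 stays in the Week 24, 36 and 48 denominators with no chance of entering the numerator, so the percentage falls as the arm shrinks.

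Some late loss is planned. Protocol 5.1.3 has subjects not responding by Week 12 withdrawn at the Investigator's discretion, without entering the extension. Early-withdrawal samples do not fully close the gap: under SAP 4.4, one mapped to a visit with no scheduled laboratory test is listed but not summarised, while the subject remains in the denominator.

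Two things are at stake. If attrition differs by arm, the arm that loses more subjects shows lower abnormality percentages for that reason alone. And one report would carry vital-sign and laboratory abnormality percentages on different bases. Safety of bimekizumab is the secondary objective, and Protocol 12.1.1.4 places neutropenia and liver enzyme changes under special monitoring.

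**Working it through.** The plan states no figure for this table, so there is nothing to reproduce. The check is a reading of every denominator statement, followed by arithmetic.

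**Which rule governs each by-visit table**

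| Table | Denominator stated locally | Rule that applies |
|---|---|---|
| Laboratory TEMA (SAP 11.3, 14.6) | None | SAP 3.1 default: Safety Set, by arm |
| Vital-sign abnormalities (SAP 11.4.1) | Yes | Subjects with a value at the visit |
| QTcF categories (SAP 11.4.2) | Yes | Subjects with a value at the visit |
| Anti-drug antibodies (SAP 10) | Yes | Observations at the visit |

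The authors wrote the exception out wherever they wanted it, which suggests that its absence from 11.3 is an oversight.

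**Formula.** Let N be the arm's Safety Set size, m the number tested at the visit, x the number with a TEMA value, and d = 1 − m/N the untested fraction.

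- Printed under the default: x/N
- Among those tested: x/m
- Ratio of the two: (x/N) ÷ (x/m) = m/N = 1 − d

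So d = 10% gives 0.90, d = 20% gives 0.80 and d = 30% gives 0.70. At d = 0 the two rules agree.

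**In counts.** SAP 2.4 raises the sample to at least 72. At 2:1 that is 72 × 2/3 = 48 on bimekizumab (BKZ) and 72 × 1/3 = 24 on certolizumab pegol (CZP). The event counts (3 and 2) and the values of d are assumptions; numbers tested are rounded to whole subjects.

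| d (assumed) | BKZ tested | 3/48 printed | 3/tested | CZP tested | 2/24 printed | 2/tested |
|---|---|---|---|---|---|---|
| 0% | 48 | 6.25% | 6.25% | 24 | 8.3% | 8.3% |
| 10% | 43 | 6.25% | 7.0% | 22 | 8.3% | 9.1% |
| 20% | 38 | 6.25% | 7.9% | 19 | 8.3% | 10.5% |
| 30% | 34 | 6.25% | 8.8% | 17 | 8.3% | 11.8% |

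**Unequal attrition.** Assume a 10% rate among those tested in both arms. With d = 10% on BKZ and 30% on CZP, the table prints 10% × 0.90 = 9.0% and 10% × 0.70 = 7.0%. With the attrition reversed it prints 7.0% and 9.0%. The documents do not say which direction is likelier. For scale, one CZP subject is 1/24 = 4.2 percentage points, more than the 2-point gap in this example.

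**The case against.** The strongest reply is that x/N is a legitimate quantity: the share of treated subjects with an observed TEMA value at that visit. SAP 11.3 counts subjects who have such a value and nowhere classifies untested subjects as normal. A reader might infer that the table understates a true abnormality rate; the documents do not support that. The shortfall is relative to the rate among those tested, and that rate has its own bias. Protocol 6.3 lists neutrophils or lymphocytes below 0.5 × 10⁹/L as withdrawal criteria, and Protocol 6.3.1 lists ALT or AST thresholds such as 5 times ULN. These lie inside the TEMA ranges of SAP Tables 14-5 and 14-6, so some subjects are absent later because of an earlier abnormality. This stands.

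Second, the information is recoverable. SAP 11.3 also summarises chemistry and hematology by arm and visit, and SAP 3.1 includes n in continuous summaries. All measurements of any variable with a TEMA result are listed for that subject. The liver abnormality table covers any post-Baseline visit, so by-visit attrition does not scale it in this way. This stands too: no individual signal is hidden. It does not explain why adjacent tables should use different bases.

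Third, a reader might extend the point to the ASDAS state table in SAP 8.2.1.2 and conclude that the arm losing more subjects looks better controlled. That is one-sided. SAP 8.2.1.1 says: "Subjects with missing ASDAS at Week 12 will not be classified in terms of their ASDAS disease activity state or improvement". Keeping those subjects in the denominator lowers every state's share. For inactive disease and major improvement, the two secondary efficacy variables, it acts like counting them as non-responders, which works against the arm with more loss. Putting only the high-activity rows on an observed-case base would place one table on two bases. The point is therefore confined to the laboratory table.

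**Conclusion.** The concern holds as a minor one. Read as written, the SAP puts the by-visit laboratory TEMA percentages on the full Safety Set and the parallel vital-sign and QTcF percentages on subjects measured at the visit. Late-visit laboratory percentages equal the rate among those tested times the fraction tested: 10% to 30% lower in relative terms if 10% to 30% are untested, and unchanged if nobody is. Arms with different attrition cannot be compared directly on this table.

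The mechanism follows from the text; the size rests on assumed attrition, since the documents give no dropout rate, arm difference or expected TEMA rate. No test, threshold or success criterion depends on the table. It would go too far to say that the plan makes either arm look safer: that needs unequal attrition, which the documents do not predict.

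**What to change.** In SAP 11.3, after the sentence that introduces the TEMA table, repeat the denominator sentence from SAP 11.4.1, so that each percentage is taken over the subjects who have a value of that variable at that visit. Print the number tested beside each percentage, so that attrition is visible and readers can judge selective loss.

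The cost is one sentence in the SAP, a denominator change in the table program and one extra column. Some printed abnormality percentages become slightly higher. The change does not bring listed-only early-withdrawal samples into the numerator, and it does not remove the bias from withdrawals triggered by laboratory values; the listings of TEMA values remain the place to see those subjects.
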